Appendix IX

Specimen Submission Instructions for Southwest Oncology Group Patients
[DELETED IN ADDENDUM #1]

Randomized Phase III Trial Comparing the Frequency of Major Erythroid Response (MER) to Treatment with Lenalidomide (Revlimid®) Alone and in Combination with Epoetin Alfa (Procrit®) in Subjects with Low- or Intermediate-1 Risk MDS and Symptomatic Anemia

Appendix X

Rev. 7/11

Lenalidomide Risks of Fetal Exposure, Pregnancy Testing Guidelines and Acceptable Birth Control Methods

Risks Associated with Pregnancy

Lenalidomide is structurally related to thalidomide. Thalidomide is a known human teratogenic active substance that causes severe life-threatening birth defects. An embryofetal development study in animals indicates that lenalidomide produced malformations in the offspring of female monkeys who received the drug during pregnancy. The teratogenic effect of lenalidomide in humans cannot be ruled out. Therefore, a risk minimization plan to prevent pregnancy must be observed.

Criteria for females of childbearing potential (FCBP)

This protocol defines a female of childbearing potential as any woman, regardless of sexual orientation, or whether they have undergone tubal ligation, who: 1) has not undergone a hysterectomy or bilateral oophorectomy or 2) has not been naturally postmenopausal (amenorrhea following cancer therapy does not rule out childbearing potential) for at least 24 consecutive months (i.e., has had menses at any time in the preceding 24 consecutive months).

Counseling

For a female of childbearing potential, lenalidomide is contraindicated unless all of the following are met (i.e., all females of childbearing potential must be counseled concerning the following risks and requirements prior to the start of lenalidomide):

- She understands the potential teratogenic risk to the unborn child
- She understands the need for effective contraception, without interruption, 4 weeks before starting study treatment, throughout the entire duration of study treatment, dose interruption and 28 days after the end of study treatment
- She should be capable of complying with effective contraceptive measures
- She is informed and understands the potential consequences of pregnancy and the need to notify her study doctor immediately if there is a risk of pregnancy
- She understands the need to commence the study treatment as soon as study drug is dispensed following a negative pregnancy test
- She understands the need and accepts to undergo pregnancy testing based on the frequency outlined in this protocol

She acknowledges that she understands the hazards and necessary precautions associated with the use of lenalidomide

The investigator must ensure that for females of childbearing potential:

- Complies with the conditions for pregnancy risk minimization, including confirmation that she has an adequate level of understanding

- Acknowledge the aforementioned requirements

For a female NOT of childbearing potential, lenalidomide is contraindicated unless all of the following are met (i.e., all females NOT of childbearing potential must be counseled concerning the following risks and requirements prior to the start of lenalidomide):

- She acknowledges that she understands the hazards and necessary precautions associated with the use of lenalidomide

Traces of lenalidomide have been found in semen. Male patients taking lenalidomide must meet the following conditions (i.e., all males must be counseled concerning the following risks and requirements prior to the start of lenalidomide):

- Understand the potential teratogenic risk if engaged in sexual activity with a pregnant female or a female of childbearing potential
- Understand the need for the use of a condom even if he has had a vasectomy, if engaged in sexual activity with a pregnant female or a female of childbearing potential.

Contraception

Females of childbearing potential (FCBP) enrolled in this protocol must agree to use two reliable forms of contraception simultaneously or to practice complete abstinence from heterosexual contact during the following time periods related to this study: 1) for at least 28 days before starting study drug; 2) while participating in the study; 3) during dose interruptions; and 4) for at least 28 days after study treatment discontinuation.

The two methods of reliable contraception must include one highly effective method and one additional effective (barrier) method. FCBP must be referred to a qualified provider of contraceptive methods if needed. The following are examples of highly effective and additional effective methods of contraception:

- Highly effective methods:
 - Intrauterine device (IUD)
 - Hormonal (birth control pills, injections, implants)
 - Tubal ligation
 - Partner's vasectomy
- Additional effective methods:
 - Male condom
 - Diaphragm
 - Cervical Cap
 - Implants and levonorgestrel-releasing intrauterine systems are associated with an increased risk of infection at the time of insertion and irregular vaginal bleeding. Prophylactic antibiotics should be considered particularly in patients with neutropenia.

Pregnancy testing

Medically supervised pregnancy tests with a minimum sensitivity of 25 mIU/mL must be performed for females of childbearing potential, including females of childbearing potential who commit to complete abstinence, as outlined below.

Before starting study drug

Female Patients:

FCBP must have two negative pregnancy tests (minimum sensitivity of 25 mIU/mL) prior to starting study drug. The first pregnancy test must be performed within 10 to 14 days prior to the start of study drug and the second pregnancy test must be performed within 24 hours prior to the start of study drug. The patient may not receive study drug until the study doctor has verified that the results of these pregnancy tests are negative.

Male Patients:

Must practice complete abstinence or agree to use a condom during sexual contact with a pregnant female or a female of childbearing potential while participating in the study, during dose interruptions and for at least 28 days following study drug discontinuation, even if he has undergone a successful vasectomy.

During study participation and for 28 days following study drug discontinuation

Female Patients:

- FCBP with regular or no menstrual cycles must agree to have pregnancy tests weekly for the first 28 days of study participation and then every 28 days while on study, at study discontinuation, and at day 28 following study drug discontinuation. If menstrual cycles are irregular, the pregnancy testing must occur weekly for the first 28 days and then every 14 days while on study, at study discontinuation, and at days 14 and 28 following study drug discontinuation.
- At each visit, the Investigator must confirm with the FCBP that she is continuing to use two reliable methods of birth control.
- Counseling about pregnancy precautions and the potential risks of fetal exposure must be conducted at a minimum of every 28 days.
- If pregnancy or a positive pregnancy test does occur in a study patient, study drug must be immediately discontinued.
- Pregnancy testing and counseling must be performed if a patient misses her period or if her pregnancy test or her menstrual bleeding is abnormal. Study treatment must be discontinued during this evaluation.
- Females must agree to abstain from breastfeeding during study participation and for at least 28 days after study drug discontinuation.

Male Patients:

- Counseling about the requirement for complete abstinence or condom use during sexual contact with a pregnant female or a female of childbearing potential and the potential risks of fetal exposure to lenalidomide must be conducted at a minimum of every 28 days.
- If pregnancy or a positive pregnancy test does occur in the partner of a male study patient during study participation, the investigator must be notified immediately.

Additional precautions

- Patients should be instructed never to give this medicinal product to another person and to return any unused capsules to the study doctor at the end of treatment.
- Female patients should not donate blood during treatment and for at least 28 days following discontinuation of lenalidomide.
- Male patients should not donate blood, semen or sperm during treatment or for at least 28 days following discontinuation of lenalidomide.
- Only enough study drug for 28 days or one cycle of therapy (whichever is shorter) may be dispensed with each cycle of therapy.

Randomized Phase III Trial Comparing the Frequency of Major Erythroid Response (MER) to Treatment with Lenalidomide (Revlimid®) Alone and in Combination with Epoetin Alfa (Procrit®) in Subjects with Low- or Intermediate-1 Risk MDS and Symptomatic Anemia

Appendix XI

Lenalidomide Education and Counseling Guidance Document

Rev. 7/11

To be completed prior to each dispensing of study drug.

Protocol Number: _____

Patient Name (Print): _____ DOB: ____/____/____ (mm/dd/yyyy)

(Check the appropriate box to indicate risk category)

Female: ☐

If female, check one:

- ☐ FCBP (Female of childbearing potential): sexually mature female who: 1) has not undergone a hysterectomy (the surgical removal of the uterus) or bilateral oophorectomy (the surgical removal of both ovaries) or 2) has not been naturally postmenopausal (amenorrhea following cancer therapy does not rule out childbearing potential) for at least 24 consecutive months (i.e., has had menses at any time during the preceding 24 consecutive months)
- ☐ NOT FCBP

Male: ☐

Do Not Dispense study drug if:

- The patient is pregnant.
- No pregnancy tests were conducted for a FCBP.
- The patient states she did not use TWO reliable methods of birth control (unless practicing complete abstinence of heterosexual contact) [at least 28 days prior to treatment, during treatment and during dose interruption].

FCBP:

1. I verified that the required pregnancy tests performed are negative.
2. I counseled FCBP regarding the following:
 - Potential risk of fetal exposure to lenalidomide: If lenalidomide is taken during pregnancy, it may cause birth defects or death to any unborn baby. Females are advised to avoid pregnancy while taking lenalidomide. The teratogenic potential of lenalidomide in humans cannot be ruled out. FCBP must agree not to become pregnant while taking lenalidomide.
 - Using TWO reliable methods of birth control at the same time or complete abstinence from heterosexual contact [at least 28 days prior to treatment, during treatment, during dose interruption and 28 days after discontinuation of lenalidomide].

- That even if she has amenorrhea she must comply with advice on contraception
- Use of one highly effective method and one additional method of birth control AT THE SAME TIME. The following are examples of highly effective and additional effective methods of contraception:
 - Highly effective methods:
 - Intrauterine device (IUD)
 - Hormonal (birth control pills, injections, implants)
 - Tubal ligation
 - Partner's vasectomy
 - Additional effective methods:
 - Male condom
 - Diaphragm
 - Cervical Cap
- Pregnancy tests before, during, and after treatment, even if the patient agrees not to have reproductive heterosexual contact. Two pregnancy tests will be performed prior to receiving study drug, one within 10 to 14 days and the second within 24 hours of the start of study drug.
- Frequency of pregnancy tests to be done:
 - Every week during the first 28 days of this study and a pregnancy test every 28 days during the patient's participation in this study if menstrual cycles are regular or every 14 days if cycles are irregular.
 - If the patient missed a period or has unusual menstrual bleeding.
 - When the patient is discontinued from the study and at day 28 after study drug discontinuation if menstrual cycles are regular. If menstrual cycles are irregular, pregnancy tests will be done at discontinuation from the study and at days 14 and 28 after study drug discontinuation.
 - Stop taking study drug immediately in the event of becoming pregnant and to call their study doctor as soon as possible.
 - NEVER share study drug with anyone else.
 - Do not donate blood while taking study drug and for 28 days after stopping study drug.
 - Do not breastfeed a baby while participating in this study and for at least 28 days after study drug discontinuation.
 - Do not break, chew, or open study drug capsules.
 - Return unused study drug to the study doctor.

3. Provide Lenalidomide Information Sheet to the patient.

FEMALE NOT OF CHILDBEARING POTENTIAL (NATURAL MENOPAUSE FOR AT LEAST 24 CONSECUTIVE MONTHS, A HYSTERECTOMY, OR BILATERAL OOPHORECTOMY):

4. I counseled the female NOT of child bearing potential regarding the following:
 - Potential risks of fetal exposure to lenalidomide (Refer to item #2 in FCBP)
 - NEVER share study drug with anyone else.
 - Do not donate blood while taking study drug and for 28 days after stopping study drug.
 - Do not break, chew, or open study drug capsules
 - Return unused study drug capsules to the study doctor.
5. Provide Lenalidomide Information Sheet to the patient.

MALE:

6. I counseled the Male patient regarding the following:
 - Potential risks of fetal exposure to lenalidomide (Refer to item #2 in FCBP).
 - To engage in complete abstinence or use a condom when engaging in sexual contact (including those who have had a vasectomy) with a pregnant female or a female of childbearing potential, while taking study drug, during dose interruptions and for 28 days after stopping study drug.
 - Males should notify their study doctor when their female partner becomes pregnant and female partners of males taking study drug should be advised to call their healthcare provider immediately if they get pregnant.
 - NEVER share study drug with anyone else.
 - Do not donate blood, semen or sperm while taking study drug and for 28 days after stopping study drug.
 - Do not break, chew, or open study drug capsules.
 - Return unused study drug capsules to the study doctor.
7. Provide Lenalidomide Information Sheet to the patient.

Counselor Name (Print): _____

Counselor Signature: _____ Date: ____/____/____

****Maintain a copy of the Lenalidomide Education and Counseling Guidance Document in the patient records****

Randomized Phase III Trial Comparing the Frequency of Major Erythroid Response (MER) to Treatment with Lenalidomide (Revlimid®) Alone and in Combination with Epoetin Alfa (Procrit®) in Subjects with Low- or Intermediate-1 Risk MDS and Symptomatic Anemia

Randomized Phase III Trial Comparing the Frequency of Major Erythroid Response (MER) to Treatment with Lenalidomide (Revlimid®) Alone and in Combination with Epoetin Alfa (Procrit®) in Subjects with Low- or Intermediate-1 Risk MDS and Symptomatic Anemia

Appendix XIII

CPPCP Site Counselor Form

Rev. 7/11, 6/14,
4/15

	
Lenalidomide Counseling Program Site Counselor Identification Form NCI Protocol#: _____ Cooperative Group Name (if applicable, ex. SWOG, ECOG) _____

---	---

- Please provide at least two (2) counselors and fax back to [contact]
- Use one form per counselor.
- Identified counselors must be a licensed healthcare professional (e.g. RN, PA, RPh, PhD, LPN, CNP or MD).
- If you have any questions, please contact [contact]

General Information

Principal Investigator: _____ Institution Name: _____

CTEP site ID: _____

Counselor Information
First Name: _____ Middle Initial: _____ Last Name: _____
License Type: (circle one) MD PhD PA CNP RN LPN RPh Other: _____
Email Address: _____
Phone: _____ Fax: _____
Institution Street Address: _____
City: _____ State/Region: _____
Zip/Post Code: _____ Country: _____
Previously approved as a _____ Counselor?  No  Yes
If Yes, which Protocol: _____

Randomized Phase III Trial Comparing the Frequency of Major Erythroid Response (MER) to Treatment with Lenalidomide (Revlimid®) Alone and in Combination with Epoetin Alfa (Procrit®) in Subjects with Low- or Intermediate-1 Risk MDS and Symptomatic Anemia

Appendix XIV

Rev. 11/13

Instructions for Reporting Pregnancies on a Clinical Trial

What needs to be reported?

All pregnancies and suspected pregnancies (including a positive or inconclusive pregnancy test regardless of age or disease state) of a female patient while she is on Lenalidomide, or within 28 days of the patient's last dose of Lenalidomide must be reported in an expeditious manner. The outcome of the pregnancy and neonatal status must also be reported.

How should the pregnancy be reported?

The pregnancy, suspected pregnancy, or positive/inconclusive pregnancy test must be reported via NCI's Adverse Event Expedited Reporting System (CTEP-AERS)
(http://ctep.cancer.gov/protocolDevelopment/electronic_applications/CTEP-AERS.htm)

When does a pregnancy, suspected pregnancy or positive/inconclusive pregnancy test need to be reported?

An initial report must be done within 24 hours of the Investigator's learning of the event, followed by a complete expedited CTEP-AERS report within 5 calendar days of the initial 24-hour report.

What other information do I need in order to complete the CTEP-AERS report for a pregnancy?

- The pregnancy (fetal exposure) must be reported as a Grade 3 "Pregnancy, puerperium and perinatal conditions – Other (pregnancy)" under the System Organ Class (SOC) "Pregnancy, puerperium and perinatal conditions"
- The pregnancy must be reported within the timeframe specified in the Adverse Event Reporting section of the protocol for a grade 3 event.
- The start date of the pregnancy should be reported as the calculated date of conception.
- The potential risk of exposure of the fetus to the investigational agent(s) or chemotherapy agent(s) should be documented in the "Description of Event" section of the CTEP-AERS report.

What else do I need to know when a pregnancy occurs to a patient?

- The Investigator must follow the female patient until completion of the pregnancy and must report the outcome of the pregnancy and neonatal status via CTEP-AERS.
- The decision on whether an individual female patient can continue protocol treatment will be made by the site physician in collaboration with the study chair and ECOG-ACRIN Operations Office - Boston. Please contact the ECOG-ACRIN Operations Office - Boston to ask for a conference call to be set up with the appropriate individuals.
- It is recommended the female subject be referred to an obstetrician-gynecologist, preferably one experienced in reproductive toxicity for further evaluation and counseling.

How should the outcome of a pregnancy be reported?

The outcome of a pregnancy should be reported as an amendment to the initial CTEP-AERS report if the outcome occurs on the same cycle of treatment as the pregnancy itself. However, if

the outcome of the pregnancy occurred on a subsequent cycle, a new CTEP-AERS report should be initiated reporting the outcome of the pregnancy.

What constitutes an abnormal outcome?

An abnormal outcome is defined as any pregnancy that results in the birth of a child with persistent or significant incapacity or substantial disruption of the ability to conduct normal life functions (formerly referred to as disabilities), congenital anomalies, or birth defects. For assistance in recording the grade or category of these events, please contact the NCI Medical Help Desk at [contact] or [contact], for it will need to be discussed on a case by case basis.

Rev. Add14 **Reporting a Pregnancy Loss**

A pregnancy loss is defined in CTCAE as “A death in utero.”

It must be reported via CTEP-AERS as Grade 4 “Pregnancy loss” under the System Organ Class (SOC) “Pregnancy, puerperium and perinatal conditions”.

A fetal death should **NOT** be reported as a Grade 5 event as currently CTEP-AERS recognizes this event as a patient’s death.

Rev. Add14 **Reporting a Neonatal Death**

A neonatal death is defined in CTCAE as “A death occurring during the first 28 days after birth” that is felt by the investigator to be at least possibly due to the investigational agent/intervention. However, for this protocol, any neonatal death that occurs within 28 days of birth, without regard to causality, must be reported via CTEP-AERS AND any infant death after 28 days that is suspected of being related to the in utero exposure to Lenalidomide must also be reported via CTEP-AERS.

It must be reported via CTEP-AERS as Grade 4 “*Death Neonatal*” under the System Organ Class (SOC) “General disorder and administration site conditions”.

A neonatal death should **NOT** be reported as a Grade 5 event as currently CTEP-AERS recognizes this event as a patient’s death.

Rev. Add15 **Additional Required Forms:**

When submitting CTEP-AERS reports for pregnancy, pregnancy loss, or neonatal loss, the CTEP 'Pregnancy Information Form' must be completed and faxed along with any additional medical information to CTEP [contact]). This form is available on CTEP's website (http://ctep.cancer.gov/protocolDevelopment/electronic_applications/docs/PregnancyReportForm.pdf)

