8.1.12 Patient Care Implications and Counseling

Risks Associated with Pregnancy

Lenalidomide is structurally related to thalidomide. Thalidomide is a known human teratogenic active substance that causes severe life-threatening birth defects. An embryofetal development study in animals indicates that lenalidomide produced malformations in the offspring of female monkeys who received the drug during pregnancy. The teratogenic effect of lenalidomide in humans cannot be ruled out. Therefore, a risk minimization plan to prevent pregnancy must be observed.

Definition of female of childbearing potential (FCBP)

This protocol defines a female of childbearing potential as any woman, regardless of sexual orientation or whether they have undergone tubal ligation, who meets the following criteria: 1) has not undergone a hysterectomy or bilateral oophorectomy or 2) has not been naturally postmenopausal (amenorrhea following cancer therapy does not rule out childbearing potential) for at least 24 consecutive months (i.e., has had menses at any time in the preceding 24 consecutive months).

Before starting study drug:

Female Subjects:

- FCBP must have two negative pregnancy tests (minimum sensitivity of 25 mIU/mL) prior to starting study drug. The first pregnancy test must be performed within 10-14 days prior to the start of study drug and the second pregnancy test must be performed within 24 hours prior to the start of study drug. The subject may not receive study drug until the Investigator has verified that the results of these pregnancy tests are negative.

Male Subjects:

- Must agree to use a latex condom during sexual contact with females of childbearing potential while participating in the study and for at least 28 days following discontinuation from the study even if he has undergone a successful vasectomy.

All Subjects:

- Only enough lenalidomide for one cycle of therapy may be dispensed with each cycle of therapy.
- If pregnancy or a positive pregnancy test does occur in a study subject or the partner of a male study subject during study participation, lenalidomide must be immediately discontinued.

Counseling

- In investigational studies where lenalidomide is supplied by the NCI, patients will be counseled by a qualified healthcare professional (including but not limited to, nurses, pharmacists and physicians). Two healthcare professionals at each site will be trained by Celgene in requirements specific to counseling of

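### Appendix XIV leaves continued treatment of a pregnant patient to an individual joint decision, while Section 8.1.12 and Appendix X require an immediate stop, and no text says which prevails

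*Combined protocol and SAP*

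**What the plan says.** Three places in the protocol say what happens to treatment when a female patient becomes pregnant.

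- **Appendix XIV** (instructions for reporting pregnancies), under the question "What else do I need to know when a pregnancy occurs to a patient": "The decision on whether an individual female patient can continue protocol treatment will be made by the site physician". It names two further parties to that decision, the study chair and the ECOG-ACRIN operations office, and tells sites to ask that office for a conference call.
- **Section 8.1.12**, in the list for all subjects, on a pregnancy or positive test: "during study participation, lenalidomide must be immediately discontinued".
- **Appendix X**, for female patients during the study: "If pregnancy or a positive pregnancy test does occur in a study patient, study drug must be immediately discontinued". For a missed period, or an abnormal test or menstrual bleeding, it adds: "Study treatment must be discontinued during this evaluation".

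Appendix XI, the counseling document, sides with the second and third. It lists pregnancy as a reason not to dispense, and has the counselor tell the patient to stop the drug immediately if she becomes pregnant.

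Two places cover the partner of a male patient. Section 8.1.12 applies its stop rule to a "study subject or the partner of a male study subject during study participation, lenalidomide must be immediately discontinued". Appendix X says that on a pregnancy or positive test "in the partner of a male study patient during study participation, the investigator must be notified immediately", and does not mention discontinuation.

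**The concern.** Section 8.1.12 and Appendix X describe a stop that is immediate and depends on nobody's judgment. Appendix XIV describes a question still open once a pregnancy has occurred, to be settled for the individual patient by three parties. A site that reads only Appendix XIV could reasonably think treatment may go on until the call has taken place. A site that reads Section 8.1.12 would stop at once. Each could say it followed the protocol.

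What is at stake is fetal exposure. Section 8.1.12 says that a teratogenic effect in humans has not been excluded and that a plan to minimize pregnancy risk has to be followed. Section 5.4 warns of birth defects or embryo-fetal death. The central instruction of such a plan should read the same wherever a site meets it.

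**Working it through.** No figure in the plan is in dispute and no arithmetic applies. The check is to set the texts side by side and ask whether any reading makes them agree.

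| Text | Trigger | Effect on treatment | Who decides |
|---|---|---|---|
| Section 8.1.12 | Pregnancy or positive test in a subject, or in a male subject's partner | Lenalidomide stopped immediately | Nobody; automatic |
| Appendix X, female patients | Pregnancy or positive test | Study drug stopped immediately | Nobody; automatic |
| Appendix X, female patients | Missed period, or abnormal test or bleeding | Stopped during evaluation | Nobody; automatic |
| Appendix XI | Patient becomes pregnant | She is told to stop; drug is not dispensed | Nobody; automatic |
| Appendix XIV | Pregnancy occurs in a patient | Open: whether she can continue | Site physician, study chair and operations office |
| Appendix X, male patients | Pregnancy or positive test in partner | Not stated; investigator notified | Not stated |

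**Step 1. Could protocol treatment in Appendix XIV mean something other than lenalidomide?** On Arm A (Section 5.1.1) protocol treatment is lenalidomide alone. On Arm B the other agent is epoetin alfa, and Section 8.2.14 says it should not be used in pregnancy. Neither arm leaves an agent to which the Appendix XIV decision could apply without meeting another rule.

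**Step 2. Could Appendix XIV concern restarting after a stop?** It speaks of continuing, not resuming. It does not first require a stop, and the question above it presupposes that a pregnancy has occurred.

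**Step 3. Is there a tie-breaker?** Appendix XIV does not refer to Section 8.1.12, Appendix X or Appendix XI. Section 5.7, on duration of therapy, does not name pregnancy among its reasons for ending treatment. Section 5.3.6 sends sites to Appendix XIV for detailed pregnancy-reporting instructions, so sites will be reading it when the event happens. The revision marks do not settle precedence: Appendix XIV is marked 11/13 and Appendix X 7/11, and nothing says that the later text governs.

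**Step 4. Partners of male patients.** A duty to notify and a duty to stop can both be met, so these texts do not exclude each other. But Appendix X has a stop rule for female patients and none for partners, so a site using it alone would not learn of the rule in Section 8.1.12. Section 9.6 projects 159 men among 252 patients (159/252 = 63%), so the partner instruction concerns the larger group.

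**Step 5. Size.** The documents give no expected pregnancy rate, no count of female patients of childbearing potential among the 93 women projected, and no data on partners. No event count can be derived.

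**The case against.** The best opposing case is that the texts run in sequence. Appendix XIV also covers suspected pregnancies, inconclusive tests and events up to 28 days after the last dose. Some of these will prove not to be pregnancies, and someone must then decide about further treatment. Appendix X itself uses discontinuation for a temporary stop during an evaluation. On this view the drug stops first and the joint decision comes later. Appendix XIV is also a reporting appendix, and the clinical rule sits elsewhere.

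Part of this stands. The sequence is a sensible practice and may be what was meant. It is not what Appendix XIV says: there is no prior stop, no limit to tests later found false, and the wording concerns continuing after a pregnancy has occurred.

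The safeguards also stand. Section 8.1 requires a negative test before lenalidomide is dispensed to a female of childbearing potential, and limits supply to 28 days. Section 8.1.12 withholds drug until counseling is documented, including verification of negative tests. Appendix XI gives both counselor and patient a stop instruction. Appendix XIV overrides none of these. They make continued exposure less likely, but they do not make the texts consistent.

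Three stronger readings are tempting and are not supported:

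- A reader might infer that the protocol as a whole permits lenalidomide in pregnancy. It does not; Section 8.1.12 and Appendices X and XI all say stop.
- A reader might infer that the site physician decides alone. Appendix XIV names the study chair and the operations office as well.
- A reader might infer that the partner texts contradict each other in the same way. Appendix X nowhere says a male patient may continue; it is silent, which is an omission.

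**Conclusion.** The concern holds for female patients. Appendix XIV leaves open a question that Section 8.1.12 and Appendix X close, and the documents provide no order of precedence. The partner point is secondary: two texts of unequal completeness that should be aligned.

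The consequence is confined to participant safety and site instruction. The endpoint, power, interim monitoring and analysis are untouched. How often the conflict would matter is unknown. One might expect few pregnancies in this disease, but that would be an assumption, since the documents give nothing to estimate it from. The case for acting rests on the severity of the harm the protocol itself describes and on the low cost of the correction.

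The conclusion assumes only that the cited sections are all current and that a site may consult any one of them alone. It takes no position on which clinical rule is right.

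**What to change.** Reconcile Appendix XIV, Section 8.1.12 and Appendix X so that all three state one rule for female patients, and have each refer to the others. If the Appendix XIV decision is meant for a narrower situation, such as a test later found to be false, the text should say so. Keep Appendix XI in step with whatever is settled.

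Separately, make Section 8.1.12 and the male-patient part of Appendix X agree on what follows a partner's pregnancy.

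The clinical team chooses both rules. The cost is about one sentence in Appendix XIV and one in Appendix X or Section 8.1.12, plus cross-references, with no change to the design, data collection or analysis.
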